6.2.2 Enrollment, Baseline, and/or Randomization

CNAs will be enrolled in the screening process after they have read the embedded consent form on the Screening Questionnaire, and have chosen to fill out the questionnaire. The Screening Questionnaire involves demographic questions as well as the Perceived Stress Scale.

For the intervention portion of the study, CNAs will be enrolled after reviewing and signing the written consent form with study staff in a one-on-one process. This process will occur up to 2 weeks before enrollment in the course begins.

Once enrolled, participants complete an in-person interview (the Baseline Interview) with study staff. This baseline interview will capture their preliminary scores on:

- Stress levels
- Attitudes towards dementia
- Job satisfaction and intent to leave job
- Burnout score
- Self-compassion score
- Depression score

6.2.3 Follow-up Visits

After initial enrollment, and collection of the Baseline Interview, CNAs will begin participating in the intervention, the CNA Wellbeing Program. There will be 8 intervention sessions, as well as a 9th session for feedback (or, 6 intervention sessions, and a 7th for feedback, if taking the 6-week version of the program). Additionally, CNAs will be approached at the End-of-Program mark, and the 3/6 month mark post course, to gather additional survey responses. These interviews will continue to capture the participants' scores on:

- Stress levels
- Attitudes towards dementia
- Job satisfaction and intent to leave job
- Burnout score
- Self-compassion scores
- Depression score

See above (in section 6.1 Schedule of Evaluations) for an exact list of what will be collected from CNAs at each point, baseline, weekly, post course, 3-months, and 6-months.

6.2.4 Completion/Final Evaluation

Study staff will continue to follow up with participants until the point of the final evaluation, the 6-month Follow Up Interview.

7 SAFETY ASSESSMENTS

Potential Risks and Benefits for Participants

Potential Risks:

The potential risks to study participants include:

- Emotional discomfort caused by study questions.
- Emotional or psychological discomfort or distress (e.g., agitation, anxiety) caused by exercises, group discussion, or home practices.
- Physical discomfort during sitting exercises.
- Emotional or economic (employment-related) harm due to breach of confidentiality. This includes breach of confidentiality regarding any personal information shared during the group intervention sessions, questionnaire data, or outcome data collected from administrative records.

Potential Benefits:

The potential benefits to study participants include:

- Stress-management skills that may improve well-being and positively impact relationships and job performance.
- Lifetime access to resources (e.g., audio guided meditations, course materials) that may help sustain well-being and stress-management skills.

7.1 Specification of Safety Parameters

This study employs a Safety Monitoring Committee (SMC), composed of 3 members in order to monitor the safety of this study. See below for details on the process by which Adverse Events/Serious Adverse Events are defined, and will be handled.

7.2 Adverse Events and Serious Adverse Events

Adverse event (AE): Any unfavorable and unintended change in physical or mental health status (i.e. new or worsening physical or mental health signs, symptoms, or disease) or loss of employment associated with participation in the study, regardless of whether it is considered related to the study.

A serious adverse event (SAE): Any AE that: results in death; is life threatening, or places the participant at immediate risk of death from the event as it occurred; requires or prolongs hospitalization; causes persistent or significant disability or incapacity; results in congenital anomalies or birth defects

Unanticipated problems (UPs): Involves risks to subjects or others to include, in general, any incident, experience, or outcome that meets all of the following criteria:

- Unexpected in terms of nature, severity, or frequency given (a) the research procedures that are described in the protocol-related documents, such as the IRB-approved research protocol and informed consent document; and (b) the characteristics of the subject population being studied;
- Related or possibly related to participation in the research (“possibly related” means there is a reasonable possibility that the incident, experience, or outcome may have been caused by the procedures involved in the research); and
- Suggests that the research places subjects or others at a greater risk of harm (including physical, psychological, economic, or social harm) than was previously known or recognized.

7.3 Reporting Procedures

Given course content can bring up difficult emotions, study staff will monitor depressive symptoms weekly. Study staff will also ask participants to report any changes in their physical health that may be

related to their participation in the study, with the exception of transient discomfort during sitting practices. Examples of potentially relevant, although unlikely, physical health changes include: headaches, body or joint aches, or an injury occurring during mindfulness practice. These examples will be given to participants, with the caveat that they should err on the side of caution and over-reporting. Additionally, in order to monitor for participants' at risk of giving birth to a child with a birth defect, the intervention instructors will report to Principal Investigator and study staff if they learn of any pregnancy within their program participants.

In order to facilitate the reporting of potential AEs to study staff, the following procedures will be in place:

[1] During the 8-week intervention period, participants will be engaged in weekly group discussions about home practice, challenges to practice, and well-being. Any participant endorsing difficulties that the course facilitators feel are potentially beyond transient or typical will be approached privately to gather details.

[2] Participants will be given study staff contact information, including study phone and e-mail addresses. Participants will be encouraged to contact study staff in the event of psychological or potentially relevant physical health concerns.

[3] At the beginning of each weekly session, and at 3 and 6-months post-intervention, we will administer a brief adverse event form, through the Weekly Questionnaire. On this form, we will collect data on any serious adverse events in the previous week, depressive symptoms via the validated 8-question PROMIS Depression Short Form and physical health changes possibly related to study participation. Regarding depressive symptoms monitoring, we will collect the PROMIS depression screen at baseline. For the purposes of this study, any participant whose PROMIS depression score moves from a lower category into the severe category (i.e. greater than or equal to a T-score of 70) will be flagged as a potential adverse event and will prompt follow up by the study team via a phone call by the study staff to gather details. Study staff will also notify the course instructors of the increased emotional distress so that extra support can be provided as needed.

The study team member receiving information from participants about a potential AE related to the study will complete an Adverse Event Form.

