7.4 Follow-up for Adverse Events

Data on AEs and UPs will be collected on an ongoing basis from study start to study completion.

General AE Procedures. The project manager or study staff will report all AEs to the PI immediately using the Adverse Event Reporting Form, after having gathered all necessary details (from the Weekly Questionnaire, as well as further communication with the participant if needed). The PI will determine the severity and the relatedness of the AE, and will confer with the SMC as needed. If the AE is serious and/or unexpected, possibly related to study participation, and suggests increased risk for participants, the procedures outlined below will also be followed.

AE reports will be collected by the project manager or study staff, summarized and de-identified. A summary report of all AEs to date will be sent to the PI and the SMC in both Phases at: 1) mid-intervention (4-week mark); 2) post-intervention (8-week mark); 3) post 3-month follow-up; 4) post 6-month follow-up.

Furthermore, all AEs will be summarized as part of the Data and Safety Monitoring Report submitted post-Phase 1 and post-Phase 2 to the SMC and NIA program officer. As per UNC IRB guidelines, all AEs will be reported to the UNC IRB during the yearly study review process.

Serious AE Procedures. The project manager or study staff will report all SAEs to the PI immediately using the Adverse Event Reporting Form, after having gathered all necessary details. For all deaths and for any SAE related or possibly related to study participation, the PI will send this report and any additional information, including corrective actions already taken, within 24 hours to the SMC chair, UNC IRB and NIA program officer. The PI will follow any additional course of action recommended by the UNC IRB, NIA, and/or SMC.

Unexpected and Related AEs/UPs with increased risk. All AEs that are deemed 1) unexpected; 2) possibly or probably related to study participation; and 3) suggests increased risk for study participants will be reported to the UNC IRB, NIA project officer, and the SMC chair within 48 hours of study team awareness of the event, using each organizations' respective reporting formats. In these reports, the PI will identify any corrective action planned or already undertaken. The PI will follow any additional course of action recommended by the UNC IRB, NIA, and/or SMC.

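### Adverse events are defined regardless of relatedness, but non-serious physical changes are asked for only if possibly study-related and no question on job loss is described, so AE counts will tend to run low

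*Protocol*

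**What the plan says.** **Definition (Protocol 7.2).** An AE is "Any unfavorable and unintended change in physical or mental health status", or loss of employment associated with participation, "regardless of whether it is considered related to the study".

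**Collection (Protocol 7.3).** Staff will "ask participants to report any changes in their physical health that may be" related to participation, "with the exception of transient discomfort during sitting practices". Participants are told that "they should err on the side of caution and over-reporting". The brief form, used at each session and at 3 and 6 months, has three components:
- serious events: "we will collect data on any serious adverse events in the previous week"
- the PROMIS depression items
- "physical health changes possibly related to study participation"

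The section then says that the team member who hears of a potential AE connected with the study completes the Adverse Event Form.

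**Assessment and reporting (Protocol 7.4).** "The PI will determine the severity and the relatedness of the AE". Summaries covering every AE to date go to the PI and the safety committee at four points: mid-intervention, post-intervention, and after the 3-month and 6-month follow-ups. AEs are also summarised for the funder's program officer and the IRB.

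The SAP describes no AE analysis.

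**The concern.** The definition and the reporting rule both treat relatedness as something judged after an event is recorded. The collection rule puts that judgement first: the participant applies it in answering the physical-health question, and the team member may apply it again in deciding whether to complete the form. For non-serious physical events, the PI then assesses a set that has already been screened on the attribute to be assessed.

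Loss of employment is a separate gap. It is named in the definition, section 7 lists employment-related harm among the risks, and retention is the goal of the randomized trial that this study prepares. None of the AE procedures in section 7.3 mentions it.

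At stake is what the safety summaries mean. A table presented as all AEs would, for non-serious physical events, be a count of those that participants thought might be due to the course. The future trial could also inherit the same form.

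**Working it through.** The documents give no AE rate, so there is no figure to reproduce. The check compares definition, collection and reporting for each type of event.

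| Type of event | In the 7.2 definition? | How 7.3 collects it | Relatedness limit at collection? |
|---|---|---|---|
| Serious event | Yes | Item on the brief form | No |
| Depressive symptoms | Yes, if new or worse | PROMIS at baseline, each session, and 3 and 6 months; flagged on a move into the severe category (T-score 70 or more) | No |
| Other non-serious mental change | Yes | Facilitators' private approach; participant's own contact with staff | None stated, but no structured item is described |
| Non-serious physical change | Yes | Item on the brief form; participant's own contact about potentially relevant concerns | **Yes** |
| Loss of employment | Yes, with a qualifying phrase | No question described; the interviews in section 6.1 list intent to leave, which is a different measure | Not asked |

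**Direction.** The definition covers physical events of any relatedness. The question covers those possibly related. The second set lies inside the first, so the limit can only remove qualifying events. The over-reporting advice widens what participants will call possibly related, but it works inside the limited question and cannot make it equal to the definition.

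**Second screen.** Even if a participant mentions an unrelated complaint, section 7.3 describes the Adverse Event Form as completed for potential AEs related to the study. Section 7.4 reports on all AEs. The two do not match.

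**Scale, as illustration only.** Protocol section 2 says that 56% of nursing assistants report at least one work-related injury in a year. Such an injury meets the definition but need not be linked to the course. Assume that an annual proportion p applies to this sample at a constant hazard over the 8 months of section 5.1:

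- Proportion with an event: q = 1 − (1 − p)^(8/12)
- Expected participants with an event: N × q
- Expected missed, if a share r is volunteered anyway: N × q × (1 − r)
- Chance of at least one missed: 1 − [1 − q(1 − r)]^N

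Planned N is 15 + 30 = 45; the cap of 20 per home gives 3 × 20 = 60.

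| p (annual) | q (8 months) | With event, N = 45 | With event, N = 60 | Missed, N = 45, r = 0.50 | Missed, N = 45, r = 0.75 | Chance of at least one missed, N = 45, r = 0.75 |
|---|---|---|---|---|---|---|
| 0.56 (Protocol section 2) | 0.4215 | 19.0 | 25.3 | 9.5 | 4.7 | 99% |
| 0.30 (assumed) | 0.2116 | 9.5 | 12.7 | 4.8 | 2.4 | 91% |
| 0.10 (assumed) | 0.0678 | 3.1 | 4.1 | 1.5 | 0.8 | 54% |

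The 56% describes nursing assistants generally and includes scratches and bruises. The lower rates, the constant hazard and the values of r are assumptions. The spread, from under 1 to 9.5 participants missed, shows why no single estimate should be quoted.

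**The case against.** The case on the other side has several parts.

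- **Much of the collection is not limited.** Serious events and depression scores are gathered whatever their cause. This stands and confines the problem mainly to non-serious physical events and job loss. A reader might infer that participants are asked about related events of every kind, or that the serious-event count is too low. The text supports neither.
- **Over-reporting is encouraged and the threshold is low.** Participants need only think a change possibly related, and the examples (headaches, body or joint aches) are broad. This stands as a reason why the loss may be small. It does not remove the mismatch.
- **Other routes exist.** Facilitators approach participants who report more than transient or typical difficulties, participants may contact staff, and AE data are collected throughout. A reader might infer that events thought unrelated never reach the PI. That is too strong: they may not reach the PI, because none of these routes asks systematically about non-serious unrelated events.
- **The definition may itself be limited.** The phrase about association with participation could qualify job loss, or the whole definition. The clause that follows sets relatedness aside, so the sentence is at best ambiguous and needs clarifying in any case.
- **The forms are not in the documents.** They may ask more than section 7.3 describes. This stands, and any statement about job loss must be conditional on the forms.
- **The consequence is modest.** This is a single-arm feasibility study. The primary outcome is self-reported intent to leave and does not depend on AE counts. The stopping reasons in section 8 concern serious or severe events possibly or definitely related to the protocol. This stands; the point concerns accurate safety reporting, not the efficacy results.

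**Conclusion.** The inconsistency holds. Sections 7.2 and 7.4 call for all AEs with relatedness judged afterwards. Section 7.3 solicits non-serious physical changes only if possibly related, links the Adverse Event Form to related events, and describes no question on loss of employment. Followed as written, the plan will tend to undercount AEs as it defines them, mainly in those two categories.

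The direction follows from the text alone. The size does not: it depends on the background event rate and on how freely participants report, and the documents give neither for this sample. A reader might infer that a set fraction of all AEs, such as half or more, goes uncounted. The documents do not support that. Any such fraction would be an assumption about physical complaints, and the AE definition also takes in mental-health changes, serious events and job loss.

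The conclusion assumes that section 7.3 describes the forms fairly and that the closing clause of the definition means what it says.

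**What to change.** Reconcile Protocol sections 7.2, 7.3 and 7.4:

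1. Word the weekly, 3-month and 6-month AE questions to ask about any new or worsened physical or mental health problem, and any loss of employment, regardless of perceived cause.
2. Have the Adverse Event Form completed for any potential AE, and leave relatedness to the PI as section 7.4 already provides.
3. Clarify in section 7.2 what the phrase on association with participation qualifies.

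Sections 4.1 and 5.1 contain remarks suggesting that the trial has already been run (the stress-score selection proved unnecessary, the retreat was not held). For data collected under the limited question, AE summaries should state that non-serious physical counts cover only events participants thought possibly related. If the forms did not ask about job loss, the summaries should also say that it was not solicited. The reworded questions should be used in the planned randomized trial.

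The cost is revised question wording, a short reporting statement, and more unrelated events to log and assess in a cohort of 45 to 60.

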6.1 Schedule of Evaluations

Measure	Pre-Course*	Course									3 Months	6 Months	
		1	2	3	4	5	6	7	8	9			
Feasibility Measures													
Attendance		X	X	X	X	X	X	X	X	X			
Attrition (Withdrawal)		X	X	X	X	X	X	X	X	X			
Audio Recording										X			
Screening Questionnaire (Demographics & PSS)	X												
Baseline Interview (JSS, Intent to Leave, ADQ, MBI, PSS, SCS, PROMIS)	X												
Weekly Questionnaire (PROMIS, Home Practice, Adverse Events)		X	X	X	X	X	X	X	X				
End-of-Program Interview (Acceptability Measure, JSS, Intent to Leave, ADQ, MBI, PSS, SCS, PROMIS, Adverse Events)									X	X			
3 Month & 6 Month Interview (JSS, Intent to Leave, ADQ, MBI, PSS, SCS, PROMIS, Adverse Events)											X	X	
Measures of Adverse Events and Safety Monitoring	Pre-Course*	Course									3 Months	6 Months	
		1	2	3	4	5	6	7	8	9			
PROMIS Depression Screen	X	X	X	X	X	X	X	X	X	X		X	X
Adverse Event Monitoring Form		X	X	X	X	X	X	X	X	X		X	X
Adverse Event Reporting Form					X				X			X	X
Nursing Home Level Data		2018			2019			2020					
Administrator Interview						X							
CMS NH Compare Website		X				X					X		
*Begins 2 weeks before onset of program													

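### The protocol's only stated look-back for serious adverse events is one week, which does not suit the 3- and 6-month contacts, and no recall period is given for the forms scheduled there

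*Protocol*

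**What the plan says.** Protocol section 7.3, item [3], sets the timing: "At the beginning of each weekly session, and at 3 and 6-months post-intervention, we will administer a brief adverse event form". It says the form is delivered through the Weekly Questionnaire, and then gives the look-back: "On this form, we will collect data on any serious adverse events in the previous week". The same form also collects the PROMIS depression items and possibly related changes in physical health. No look-back is attached to the physical health question. Neither the Protocol nor the SAP states any other recall period for adverse events.

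The schedule in section 6.1 is laid out differently. The row "Weekly Questionnaire (PROMIS, Home Practice, Adverse Events" is marked in the course weeks only. At 3 and 6 months the schedule marks the row "3 Month & 6 Month Interview (JSS, Intent to Leave, ADQ, MBI, PSS, SCS, PROMIS, Adverse Events" and a separate "Adverse Event Monitoring Form", with no recall period for either. The End-of-Program Interview also has an adverse events component, and the monitoring form is marked at week 9, the feedback session.

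Section 7.4 states the intended coverage: "Data on AEs and UPs will be collected on an ongoing basis from study start to study completion". It also promises cumulative reporting: "A summary report of all AEs to date will be sent to the PI and the SMC in both Phases", with two of the four reports due after the 3-month and 6-month follow-ups.

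**The concern.** A one-week look-back works when participants are asked every week and absentees are telephoned, as section 9.1 provides. It does not work when the next contact is about three months away. If staff followed the stated wording at 3 and 6 months, an SAE that fell outside those two weeks would reach the follow-up summaries mainly if the participant volunteered it. The principal investigator can judge severity and relatedness only for events that reach the study team.

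The stake is how the follow-up safety record can be read. Section 8 lists a single possibly or definitely related SAE in any participant among the reasons for stopping the study, so one unreported event can matter to the safety review. A follow-up count of zero, collected with a one-week question, could not be read as an absence of events. The protocol also leaves staff unsure which form carries the SAE question once the course is over.

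**Working it through.** The plan gives no figure to reproduce. The check has two parts: a comparison of the sections, then the coverage that follows from a literal reading.

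**Comparison for the 3- and 6-month contacts**

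| Source | Instrument | SAE recall period |
|---|---|---|
| Section 7.3, item [3] | Brief adverse event form, through the Weekly Questionnaire | One week |
| Section 6.1 | Adverse events item in the 3/6-month interview | None stated |
| Section 6.1 | Adverse Event Monitoring Form | None stated |
| Section 9.1, 3/6-month interview | Interview, within 2 weeks either side of the mark | None stated |
| Section 7.4 | Ongoing collection; cumulative summaries | A collection period, not a recall period |

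The Adverse Event Reporting Form is also marked at these contacts. Section 7.4 shows that staff use it to report to the principal investigator, so it is not a question put to the participant. The monitoring form may be the brief form of section 7.3 under another name, but the documents do not say so.

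**Coverage on a literal reading**

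Inputs:
- One-week SAE look-back (section 7.3).
- Interviews at 3 and 6 months after the course, within 2 weeks either side (section 9.1).
- Assumptions: 3 months = 13 weeks, 6 months = 26 weeks; both interviews completed; each contact covers one week; the week-9 form and the End-of-Program Interview count together as one contact that covers one post-course week.

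Formula: share of weeks without an SAE-specific question = (T − k)/T, where T is post-course weeks to the 6-month interview and k is the number of weeks covered.

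| 6-month interview | T | k = 3 (with End-of-Program contact) | k = 2 (without) |
|---|---|---|---|
| 2 weeks early | 24 | 21/24 = 87.5% | 22/24 = 91.7% |
| On time | 26 | 23/26 = 88.5% | 24/26 = 92.3% |
| 2 weeks late | 28 | 25/28 = 89.3% | 26/28 = 92.9% |

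The column k = 3 is the better base case, because section 6.1 schedules a contact at the feedback session after the last class. The column k = 2 applies if the contact adds no post-course week, for example when the interview is held straight after the last class.

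Uncovered stretches for k = 3, on time: 13 − 1 − 1 = 11 weeks before the 3-month interview, and 13 − 1 = 12 weeks between the two interviews. Check: 11 + 12 = 23.

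These are shares of follow-up time. The documents give no SAE rate and no rate of spontaneous reporting, so the share of events missed cannot be derived.

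**The case against.** The strongest reply is that look-backs are normally fixed on the form itself, and the forms are not in the documents. If the 3- and 6-month instruments differ from the weekly form, the one-week wording need not govern them and the 88% does not apply. If they are the same form, the disagreement between sections 6.1 and 7.3 is largely one of naming. This stands as a limit on the size. It does not remove the point: section 7.3 itself extends the brief form to 3 and 6 months, and no other recall period is written anywhere.

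There are also real safeguards. The question on possibly related physical health changes has no stated look-back, so a serious physical event could surface there. Section 7.3 asks participants to report too much rather than too little about physical changes, and invites them to contact staff about psychological concerns as well. These narrow the gap. They do not replace an SAE question that covers the whole interval.

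The effect on decisions is limited too. Participants in follow-up have finished the course, and after Phase 2 no course remains to be stopped. That leaves follow-up after Phase 1, and the reading of the final safety record.

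Two stronger readings are tempting. A reader might infer that the protocol restricts follow-up ascertainment to one week, so that about 88% of SAEs would be missed. The documents support neither step: section 7.4 states continuous collection, and a share of time is not a share of events. A reader might also take the remark in section 7.4 that details come "from the Weekly Questionnaire, as well as further communication with the participant if needed" to make that questionnaire the main route for SAEs. It stands in the paragraph on general adverse events. The paragraph on serious events names no source.

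**Conclusion.** The point holds as a gap in specification with a plausible effect on safety capture. The only stated SAE look-back is one week, the protocol applies it to contacts about 13 weeks apart, and the schedule names other instruments there without a recall period. That does not fit the stated aim of continuous collection and cumulative summaries.

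On the literal reading, about 88% of post-course time (23 of 26 weeks) has no SAE-specific question, with a range of 87.5% to 92.9% across the visit windows and with or without the End-of-Program contact. This rests on one covered week per contact and on both interviews being completed. The documents do not show that any event was missed, and a longer recall on the actual forms would close the gap. The issue is confined to the period after the course.

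**What to change.** - Reconcile sections 6.1 and 7.3: say which instrument carries the SAE question at 3 and 6 months, and whether the Adverse Event Monitoring Form is the brief form of section 7.3.
- Have the End-of-Program, 3-month and 6-month contacts ask about adverse events since the last study contact. Keep the one-week look-back for the weekly sessions.
- If follow-up is complete, as the closing remark of section 4.1 suggests, state the recall window actually used and report follow-up AE and SAE counts separately from in-course counts. If the window was one week, say that a zero follow-up count does not mean that no events occurred.

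Cost: if follow-up is still open, new wording on interviews already scheduled and a minor IRB modification; if it is complete, one or two sentences and a split count in the safety report. The downside of the new wording is a longer recall period and a few more unrelated events to log.

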8 INTERVENTION DISCONTINUATION

We will prepare interim analyses to evaluate the safety of the intervention after Phase 1 and again after Phase 2. One of the tasks of the Safety Monitoring Committee (SMC) will be to review preliminary data from the study and make a recommendation RE whether or not the study should continue. The following are the reasons we propose for discontinuing the study early:

- The occurrence of a serious adverse event, possibly or definitely related to the study protocol, occurring in any participant. In this study, it would include serious psychological distress causing death, suicide attempt, or hospitalization.
- Severe adverse events, possibly or definitely related to the study protocol, occurring in 3 or more participants. In this study, this would include participants who withdrew from the study due to new psychological symptoms or who were hospitalized for mental health treatment. Given the high-stress nature of the participants jobs and lives, and given MSC involves prompting participants to become aware of and attend to their own needs, it is possible that study participation prompts mental health care that had been needed previously, but was perhaps ignored or not prioritized. Thus, severe cases will be examined carefully by the PI and SMC to determine if the cases warrant study discontinuation.
- Interim analyses will provide summary data related to the above bullets and study staff will make these data available to the SMC at least 2 weeks before meeting, or within 24 hours

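### As described, the adverse-event form does not ask about non-serious distress other than depression, although the Protocol names anxiety and agitation as risks, so such events may be under-ascertained

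*Protocol*

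**What the plan says.** The Protocol's risk list (Section 7) includes "Emotional or psychological discomfort or distress (e.g., agitation, anxiety) caused by exercises, group discussion, or home practices". Section 7.2 defines an adverse event broadly, starting from "Any unfavorable and unintended change in physical or mental health status", and does not require relatedness to the study.

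Section 7.3 sets out three procedures for bringing potential adverse events to staff:

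- **Item [1], group discussion.** "During the 8-week intervention period, participants will be engaged in weekly group discussions about home practice, challenges to practice, and well-being". It continues: "Any participant endorsing difficulties that the course facilitators feel are potentially beyond transient or typical will be approached privately to gather details".
- **Item [2], self-report.** Participants receive staff contact details and are encouraged to use them for psychological or relevant physical concerns.
- **Item [3], the form.** It is given at each weekly session and at 3 and 6 months. "On this form, we will collect data on any serious adverse events in the previous week", together with "depressive symptoms via the validated 8-question PROMIS Depression Short Form and physical health changes possibly related to study participation". The only psychological flag stated for it is "any participant whose PROMIS depression score moves from a lower category into the severe category", meaning a T-score of 70 or more.

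The schedule in Section 6.1 lists an adverse-event component in the Weekly Questionnaire, the End-of-Program Interview and the 3- and 6-month interviews. Section 7.4 sends cumulative adverse-event summaries to the principal investigator and the Safety Monitoring Committee at mid-intervention, post-intervention, and after the 3- and 6-month follow-ups, in both phases.

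**The concern.** The structured part of safety collection is narrower than both the Protocol's list of expected harms and its definition of an adverse event. The missing part is non-serious psychological reaction other than depression, which is among the more plausible harms of a meditation and self-compassion course.

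The contrast with physical harm is telling. Section 7.3 regards physical changes as unlikely, yet gives them a direct enquiry, worked examples and advice to report too much rather than too little. It also acknowledges that course content may stir difficult emotions, but the structured response is confined to depressive symptoms.

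At stake is how the safety summaries can be read. If few anxiety or agitation events appear, the committee could not tell whether few occurred or few were asked about. The same ambiguity would carry into the randomised trial that this study is meant to prepare (Section 3).

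**Working it through.** No formula applies, and the plan states no figure to reproduce. The check follows one kind of event, a non-serious episode of anxiety or agitation without marked depression, through each route in the Protocol.

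1. **Is it an expected risk?** Yes. Section 7 gives agitation and anxiety as examples.
2. **Is it an adverse event?** Yes, if new or worsening. Section 7.2 covers mental-health signs and symptoms regardless of relatedness.
3. **Does the form's serious-event part pick it up?** No. By construction it does not meet the seriousness criteria in Section 7.2.
4. **Does the PROMIS part pick it up?** Not directly. The instrument measures depression, and the stated flag is a move into the severe category.
5. **Does the physical-change part pick it up?** Not unless the reaction also shows itself as a physical complaint.
6. **Does group discussion pick it up?** Possibly. The participant must raise the difficulty in a group, and the facilitators must judge it more than transient or typical. Participants work at the same home, and Section 7 itself lists employment-related harm from breach of confidentiality about what is shared in sessions, a plausible reason for reticence. A participant who misses a session is not in that discussion. The procedure covers the intervention period only.
7. **Does self-report to staff pick it up?** Possibly. Psychological concerns are expressly invited, but the participant must take the initiative.
8. **Do other measures pick it up?** The Perceived Stress Scale and the Maslach Burnout Inventory are collected at the interviews (Section 6.1), but as outcomes. No adverse-event trigger is stated for either.

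The stated routes for this event, by period, are therefore:

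| Period | Structured question | Facilitator judgement | Spontaneous contact |
|---|---|---|---|
| During the course | none described | yes | yes |
| 3 and 6 months | none described | no | yes |

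On size, the planned sample is 15 + 30 = 45 nursing assistants, so any event count will be small. The documents give no expected rate for these reactions and no proportion captured by any route, so the shortfall cannot be computed.

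**The case against.** The strongest reply is that the form is one of three procedures presented together. Group discussion prompts participants every week about challenges and well-being, and self-report explicitly invites psychological concerns. Serious distress falls under the form's serious-event question. This stands. A reader might infer that such distress is never asked about and is bound to be under-counted, and the documents do not support that.

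The wording of the form is also not shown. Section 6.1 lists the adverse-event component separately from PROMIS, and Section 7.3 gives only a prose description. Absentees are phoned, and the later interviews are conducted by staff in person or by phone (Section 9.1), so an open question could be put there. This stands too: the point concerns the form as described, and a broader question cannot be ruled out. If one exists, the Protocol should say so.

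A reader might further infer that the count behind the early-discontinuation reasons in Section 8 will be too low, since those reasons mention "participants who withdrew from the study due to new psychological symptoms". That does not follow. The criterion concerns severe events, exemplified by withdrawal or hospitalization. Withdrawal is tracked as attrition at each session (Section 6.1), and hospitalization is a serious event, which the form asks about. Milder anxiety that goes unrecorded does not enter that count.

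Finally, a general question will gather ordinary stress in a heavily stressed workforce with no comparison arm. That is a real cost, but it bears on how events are assessed after they are reported rather than on whether to ask.

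**Conclusion.** The concern holds in a limited form. As Section 7.3 describes it, the form does not systematically solicit non-serious, non-depressive distress, although Section 7 names such distress as a risk and Section 7.2 makes it reportable. Capture rests on facilitator judgement and spontaneous contact during the course, and on spontaneous contact alone afterwards. Such events may therefore be under-ascertained in the Section 7.4 summaries, most clearly at 3 and 6 months.

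The conclusion assumes that the form contains what Section 7.3 says and nothing broader. No numerical size is attached, because any figure would depend on event and capture rates that the documents do not contain. The existing routes keep this from being a failure of safety monitoring. It is a gap between named risks and structured collection that is cheap to close.

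**What to change.** Add one item to the adverse-event component of the Weekly Questionnaire (including the version for absentees), the End-of-Program Interview and the 3- and 6-month interviews. It could read: *Since the last form, have you had any new or worse emotional or psychological difficulty, for example anxiety, agitation or distress?* The answer would be yes or no, with space to describe. Give it the same encouragement to over-report as the physical-change enquiry, assess each yes as a potential adverse event under Section 7.4, and amend the description in Section 7.3 to match. If the form already has such an item, only that amendment is needed.

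The cost is one question on instruments already in use, plus the work of logging and assessing more events. Most would be mild, and some would reflect background stress that a single-arm study cannot separate from an effect of the course.

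Parts of the Protocol are written in retrospect (Section 4.1 refers to completion of the trial). If data collection has ended, the safety report should state that these reactions were not systematically solicited, and the item should go into the planned randomised trial.
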